On a subset of ~15 patients (based on budget constraints) a brain MRI scan may also be performed during follow-up appointments. If an individual is not able to participate in the MRI scan for any reason, they will not be excluded from the study. Subject can choose not to participate in the follow-up MRI scan. MRI scan that is done solely for study purposes will not be billed to subject's insurance. Incidental findings, if any, will be shared with the subject (and their LAR, if applicable) and documented in their medical records.

Pregnant persons will be excluded in this study. Persons of childbearing age will be questioned regarding pregnancy in addition to undergoing a urine pregnancy test before MRI scan. If the urine pregnancy test is

positive, the subject will be excluded. Subjects will be told the results. Because full confidentiality regarding pregnancy cannot be entirely guaranteed, these testing requirements and the limited scope of confidentiality will be made known to the subject during the consent procedure. In this manner, anyone who would not be comfortable with pregnancy testing or sharing the results of such testing can “opt out” of the study at the time of the initial consent, without having to declare any specific reasons.

For control subjects, we will not obtain their individual MRI scans. Instead, we will use the standard brain atlas (<https://www.mcgill.ca/bic/software/tools-data-analysis/anatomical-mri/atlas/mni-305>) for the hdEEG analysis.

3) Long-term hdEEG study (Epilepsy)

Patients with epilepsy admitted to the Epilepsy Monitoring Unit (EMU) will be consented to participate in this study on one of the days of his/her admission. A 128-channel (or 256-channel) long-term monitoring (LTM) net (gel-based) will be placed on the patient’s head in the EMU. hdEEG will be recorded overnight in addition to the clinical video-EEG. There will be no control subject enrolled in this study. We expect the experiment will be completed in 6-24 hours, depending on the subject’s specific situation. A special type of photograph of the EEG cap, other electrodes and patient’s head will be taken using either the Photogrammetry system in 3C or a portable optical scanning unit described previously.

hdEEG Data Management

The primary form of data analysis will be the extraction and localization of event- or task-related EEG signals using synchronous averaging and other more sophisticated forms of signal extraction.

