Statistical Analyses. Metrics from EEG, EIT, and EIS analyses will be used for structural and functional assessment. **Structural:** We will use Receiver-Operator Characteristic (ROC) curve analysis to produce clinical metrics (area under the curve, true and false positive rates, true and false negative rates, sensitivity, specificity, positive predictive value, negative predictive value, accuracy, etc.) for the detection testing (discriminating stroke type). Accuracy (position errors) will be used to assess stroke localization. Linear regression will be used to correlate metrics/electrical properties with volume and R^2 and p-values will define the goodness of fit. **Functional:** We will explicitly evaluate linear and multi-parameter regression models as part of our analysis (including correlation, p-values, and standard deviations of residuals). Comparisons will be made between hdEEG, EIT, and EIS techniques and SSEP metrics to determine which provides the most information or if they provide complementary information through multiple linear regression and/or analysis of variance (ANOVA).

5. Study Progress Monitoring

Note: appropriate monitoring may include periodic assessment of the following:

- data quality
- timelines
- recruitment and enrollment

Provide a description of the methods which will be used to determine the progress of the study, including periodic assessments of data quality, timelines, recruitment, and enrollment as appropriate:

The PI and co-investigators will periodically review progress of the experimental testing, including assessments of data quality, patient recruitment, and progress toward validation of test effectiveness. Adverse reactions or problems with the testing performed at DHMC or reported by others will be addressed immediately and reported to the Dartmouth-Hitchcock Health Institutional Review Board (D-HH IRB).

6. Risks & Benefits

Note: Risks may be physical, psychological, social, legal, economic, to reputation, or others.

a. Describe any potential risks, their likelihood and seriousness:

This study will not create additional risk to patients with neurological disorders due to the hdEEG recording, and may result in only minimal risk associated with electrical impedance measurements.

hdEEG

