8. Placebo Use or Inconsistency with Standard of Care

Does any part of this study involve the use of a placebo or procedures that are inconsistent with the standard of care at Dartmouth-Hitchcock Medical Center?

No Yes

If Yes, explain how the use of placebo or non-standard of care therapy may affect risks for participants, addressing the following:

- The safety and efficacy of other available therapies
- The maximum total length of time a participant may receive placebo on study
- The greatest potential harm that may result from not receiving or delaying effective therapy
- Safeguards for the participants receiving placebo or non-standard of care therapy

9. Genetics

Does any part of the study involve genetic analysis of biological specimens?

No

Yes, the study is based on the premise that a link between a genotype or a biomarker and a specific disease or condition is clinically useful in predicting the development of that specific disease or condition.

Please complete the [Genetic Research Form](#) and upload it to the ‘Supporting Documents’ page in Report.

-OR -

Yes, the study is looking for an association between a genotype or a biomarker and a specific disease or condition, but at this point it is not clear if the genetic marker has predictive value. The uncertainty regarding the predictive value of the genetic marker is such that studies in this category will not involve referral of participants to genetic counseling; however, participants will be informed of genetic testing in the consent form. **Please comment:**

10. Equitable Participant Selection

a. Estimated number of participants at Dartmouth CPHS reviewed sites:

For the short-term hdEEG study: 100 epilepsy patients, 15-20 brain tumor patients and 15-20 normal controls. For the short-term stroke study: 50 EIT/EIS-measured patients with 50 controls. For the long-term study: 20 epilepsy patients. For the peripheral nerve study: 20 subjects.

b. Provide a justification of the proposed sample size

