After completing pilot studies, we will focus on those tests which appear to be eliciting consistent, localized brain activation. Under these circumstances adequate statistical power should be obtained by repeating these tests in 15-20 patients. However, for the short-term epilepsy study we are more interested in investigating the correlation between the spike localizations and other clinical diagnostic results. Due to their very deep location, the determination of spike localization could be challenging in some epilepsy patients. In order to have a better understanding of the efficacy of using high-density EEG to provide useful information for various types of epilepsy patients (i.e., temporal vs. extra-temporal), we would like to perform this study on a larger patient size.

For the EIT/EIS cohort, sample size is based on previous contrasts observed in ex-vivo ischemic and hemorrhagic tissue [a]; specifically, the conductivities at 1 kHz were 0.075 Siemens/meter (S/m) for hemorrhagic tissue and 0.11 S/m for ischemic tissue. For a reported standard deviation of 0.025 S/m, there would be a 95% power to detect significant differences through an unpaired t-test with a group sample size of ten subjects for each cohort (20 total). An initial investigation into non-invasive in-vivo signals results in an ~50% drop in signal, requiring a 2x increase in sample size and a total desired cohort of n=50, split into two sub-cohorts of n=25 ischemic and hemorrhagic stroke, respectively. However, as this is a pilot study, these are projections; should initial data indicate higher signal contrast and lower standard deviations than anticipated, the numbers will be revisited to ensure optimized patient recruitment.

[a] Yang, L., Zhang, G., Song, J., Dai, M., Xu, C., Dong, X., & Fu, F. (2016). Ex-Vivo Characterization of Bioimpedance Spectroscopy of Normal, Ischemic and Hemorrhagic Rabbit Brain Tissue at Frequencies from 10 Hz to 1 MHz. *Sensors (Basel, Switzerland)*, 16(11).

c. Define the target population:

Epilepsy patients

Patients with a diagnosis of epilepsy will be considered for participation if they are interested and in the judgment of the research team they require further mapping or are capable of performing the functional and/or cognitive tasks required of the study.

Inclusion criteria:

1. Able to perform the tasks
2. Subject or legally authorized representative able to provide appropriate consent

Exclusion criteria:

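### R² and the slope p-value are made the measure of fit for the regression on volume, but neither can show whether a straight line is adequate (minor)

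*Combined protocol and SAP*

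**What the plan says.** Section 4, Statistical Analyses, sets the rule for the structural metrics: "Linear regression will be used to correlate metrics/electrical properties with volume and R^2 and p-values will define the goodness of fit". No threshold is given for either quantity. No residual plot, linearity check, transformation or alternative curve is named for this regression.

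The functional models that follow have a slightly longer list of outputs, "including correlation, p-values, and standard deviations of residuals", but that list is not applied to the volume regression.

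The number of stroke patients comes from Section 10a, "50 EIT/EIS-measured patients with 50 controls", and Section 10b has them "split into two sub-cohorts of n=25 ischemic and hemorrhagic stroke, respectively". The source of the volume measurement is not specified. Section 3 adds a smaller possible group: "On a subset of ~15 patients (based on budget constraints) a brain MRI scan may also be performed during follow-up appointments". Section 10b also says that "as this is a pilot study, these are projections".

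**The concern.** Goodness of fit asks whether the chosen model describes the data adequately. The p-value of a simple linear regression asks something else, namely whether the slope differs from zero. It can be very small when the relation is clearly curved, and large when a straight line is correct but the data are noisy. R² says how much of the variance the line accounts for. A curved relation can give a respectable R², and a truly linear one a low R².

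The plan therefore names two numbers as the measure of fit when neither measures it. A curved relation is plausible, since a boundary impedance signal need not grow in proportion to lesion volume and lesion volumes may be right-skewed. Both are assumptions, as the documents describe neither. At stake is the description of how each metric relates to volume. A pilot that develops algorithms is where that form should be learned, and the stated rule would not reveal a wrong form.

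**Working it through.** **No figure to reproduce.** The plan gives no alpha, cut-off, expected R² or volume distribution for this regression.

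**Inputs.** n = 50 stroke patients (Section 10a); n = 25 if fitted within one stroke type (Section 10b); n of about 15 as a bounding case if volume came only from the follow-up MRI subset (Section 3). Two-sided 0.05 is assumed, because Section 10b says only that "there would be a 95% power to detect significant differences through an unpaired t-test" and gives no significance level.

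**Step 1: the p-value adds no information on shape.** In simple regression F = R²(n−2)/(1−R²) on 1 and n−2 degrees of freedom. Once R² and n are known, p is known. Solving for the R² at which p = 0.05 gives R² = t²/(t² + n − 2), with t the 97.5% point on n−2 degrees of freedom:

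| n | t | R² at p = 0.05 | Residual SD / raw SD = √(1−R²) |
|---|---|---|---|
| 50 | 2.011 | 4.043/(4.043+48) = 0.078 | 0.960 |
| 25 | 2.069 | 4.279/(4.279+23) = 0.157 | 0.918 |
| 15 | 2.160 | 4.667/(4.667+13) = 0.264 | 0.858 |

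At n=50 a significant line can leave 92% of the variance unexplained (1 − 0.078). The last column also shows that residual SD follows from R² and the raw SD. Adding it, as for the functional models, would not test shape.

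**Step 2: what a wrong line can look like.** These are simulations in which everything except n is assumed. Volume is log-normal with log-SD 1.0 or 1.4. The true relation is cube-root, logarithmic or saturating, the true curve explains 50% or 70% of the variance, and n = 50.

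- The wrong straight line has p<0.05 in 96–100% of runs, with mean R² of 0.25–0.60.
- If R² ≥ 0.5 is also required (an illustrative cut-off), the wrong line passes in 1–88% of runs, and in fewer than half the runs in 10 of the 12 scenarios.
- R² can fail to separate right from wrong. With log-SD 1.0 and true R² 0.7, a straight line fitted to a cube-root relation has mean R² of about 0.60. Fitted to a truly linear relation it has about 0.63.
- An added quadratic term flags the wrong line in 58–100% of runs, and a truly linear relation in 4–6%.

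**Step 3: sensitivity to the assumptions.** With uniform volumes:

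- A symmetric hump gives p<0.05 in only 5–11% of runs at either n.
- Weak monotone curves (true R² 0.1) give p<0.05 in 49–59% of runs at n=50 and 24–32% at n=25.
- In the other direction, a correct linear model with true R² 0.1 has p≥0.05 in 38% of runs at n=50 and 66% at n=25.

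**Step 4: limits of a quadratic check.** In the log-normal scenarios at n=25 it flags 26–90% of wrong lines. With uniform volumes at n=50 and true R² 0.5 it flags 37% of cube-root relations, 40% of squares and 6% of steps.

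**The case against.** The strongest reply is that the sentence sets out to correlate metrics with volume. R² and a slope p-value are ordinary outputs for that association aim, and the text nowhere asks whether the relation is linear. In the scenarios above every metric really is related to volume, so a significant slope is a correct detection of association and the 96–100% is power, not an error rate. R² is reported beside p and would show how much the line leaves unexplained. Section 4 also plans an EIS comparison of larger with smaller infarcts, which assumes no straight line.

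Much of this stands, and it rules out stronger readings that a reader might infer:

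- *A wrong line would be called a good fit in most cases.* The plan states no cut-off, so no fit is yet called good. The frequency runs from about 5% to about 100% with shape, noise and n, none of which is given.
- *Volume would be read back from the line, with bias.* The plan does not propose this, and estimating volume is not one of the three stroke aims in Section 4 (discriminating type, monitoring, predicting outcome).
- *Metrics would be ranked by this regression.* The comparison of techniques is a separate functional analysis by multiple regression or ANOVA.

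What the reply does not remove is the stated criterion itself. The plan goes beyond listing R² and p as outputs. It makes them the definition of fit, and they cannot serve as that.

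**Conclusion.** The point holds as a wrongly stated criterion. That the p-value tests only a zero slope, and that R² does not test shape, needs no assumption. The critical R² values of 0.078 (n=50) and 0.157 (n=25) rest only on a two-sided 0.05 level and on all patients in the group having a usable volume. The simulated percentages illustrate what can happen under assumed curves and volume distributions. They do not estimate an error rate for this study.

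Priority is minor. The analysis is exploratory, the study is a pilot whose sample size rests on a comparison of stroke types, and no decision rule depends on the volume regression.

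**What to change.** Replace the sentence in Section 4 so that it says:

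1. The p-value tests association with volume only.
2. The slope with its 95% CI and R² are reported as measures of size and strength of association.
3. Fit is judged by residual plots plus one pre-stated shape check, using leave-one-out error: volume against log-volume as predictor, or the straight line against the line with an added quadratic term. The metric stays as the response, so that the errors are on one scale.
4. The better-fitting form is reported.

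The cost is one sentence and a few lines of code on data already planned. There are two small downsides. Some metrics with significant slopes will no longer be described as fitting well. The shape check also has limited power with 25 patients and for step-like relations, so the residual plots are needed alongside it and a clean check should not be reported as proof of linearity.

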hdEEG: We plan to localize the sources of interictal epileptiform activity during resting state for patients with seizures, and map brain activity during presentation of tasks. The development, testing and refinement

of the various tasks will be an ongoing process of multidisciplinary collaboration among a variety of co-investigators representing the Department of Psychiatry ([name]), Department of Neurology ([name], [name], [name], [name], [name], [name]), and Section of Neurosurgery ([name], [name], and [name]). Testing will investigate the localization of a wide variety of brain functions, including: sensation, movement, hearing, vision, speech, memory, social cognition, and emotion. As such, a variety of hypotheses regarding the localization of specialized brain functions and their disruption by certain neurological disorder processes will be evaluated in the course of this work. The purpose of this study is to use the hdEEG for improved localization of critical brain functions important for further understanding of the brain in health and disease, and also planning surgical intervention if warranted.

EIT/EIS: EIT and EIS represent promising technologies to image or characterize the brains of stroke patients because there are significant conductivity differences between normal, ischemic, and hemorrhagic (blood) tissue. This electrical information may help to 1) identify the onset of a stroke, 2) discriminate hemorrhagic from ischemic stroke, 3) provide reliable automatic and continuous monitoring of stroke patients after stabilization aims will be an ongoing process of multidisciplinary collaboration among co-investigators representing the Department of Neurology ([name], [name], [name], [name], [name], [name]) and the Thayer School of Engineering ([name], [name], [name]).

3. Study Design

Describe all study procedures, materials, and methods of data collection:

hdEEG System: High-density EEG recordings will be obtained via the EGI Geodesic EEG 400 designed for research applications. This system is available through the Department of Neurology and Department of Psychiatry at DHMC. This EEG system uses a 256 (or 128) channel cap to record EEG signals during the resting state and during the performance of functional or cognitive tasks.

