For some experiments, normal controls will be enrolled and their test and task scores will be used for comparison purposes. EEG data will be collected from these participants.

We will be presenting participants with a variety of tasks designed to activate regions important for language, motor, sensory, auditory, visuospatial, emotion, social cognition or memory function. The tasks used will depend on the specific situation of the patient, region of seizure onset or lesion, or type of surgical procedure planned. For instance, if patient has left frontal lobe epilepsy, language tasks may be given for characterization and localization of language areas.

In order to map the motor and sensory areas, we will ask the patient to tap their fingers on the thigh periodically during the movement task. By doing so, the mu-rhythm (8-12 Hz) will predominantly appear around the primary motor and sensory cortices. However, such activity can be easily affected by artifact and is not specific to any type of movement (i.e., arms or legs). Peripheral nerve somatosensory evoked potential (SSEP) tests will also be conducted in order to reliably activate the somatosensory area during the sensory task. A clinical evoked potential recording system (i.e., Medtronic NIM E4) will be used to send a constant current stimulus through surface electrodes to subjects’ peripheral nerves (i.e., ulnar, median, tibial, etc.). The stimulation parameters used to trigger the somatosensory evoked potential will follow the ACNS guideline (<https://www.acns.org/pdf/guidelines/Guideline-9A.pdf>). The SSEP raw data will be recorded using the hdEEG system. Other potential tasks to be used in this study will be to ask patients to speak, read, name pictures, remember words, remember actions and shapes, and to view shapes or objects. At certain instances, patients may be asked to view emotionally charged pictures or videos. Using these images is important to study and localize social and emotional brain function. For instance, the type of pictures presented may include selected pictures taken from IAPS (International Affective Picture System, <https://pdfs.semanticscholar.org/09bb/229a610acdd3150b8e0176194e7b7cf471b7.pdf>). In all tasks, only pictures and/or videos specifically vetted by the IRB will be presented.

De-identified EEG data and images collected for this study will be shared with other institutions and added to public databases of EEG data. All data released will be de-identified.

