EEG data will be exported and pre-processed by Matlab programs developed in-house. The global field potential (GFP) and entropy across all 256 or 128 channels will be computed at each time point. GFP is sensitive to polarity changes across channels, while entropy could be helpful to eliminate EMG artifacts. Interictal epileptiform discharges (IEDs) will be identified by auto-thresholding both GFP and entropy. The source localization of IEDs will be determined using inverse solutions in Brainstorm. If applicable, intracranial EEG and/or intraoperative ECoG recordings will be used to evaluate the accuracy of IED source localizations. In addition to the self-developed detection algorithm, we will also utilize Spike Beacon software, which is developed by EGI to detect interictal discharges and compare it with our own algorithms.

For each subject, the EEG signals will be analyzed in 84 regions of interest (ROIs) defined according to the 42 Brodmann areas (BAs) for the left and right hemispheres. These ROIs will be defined for each subject using FreeSurfer. Low resolution electromagnetic tomographic analysis (LORETA) will be used to inversely estimate the EEG signal from these ROIs to localize cortical and subcortical sources from EEG signal generators. The EEG data will be investigated in the following aspects: 1) frequency content, including relative composition of delta (0.5-3 Hz), theta (3-7 Hz), alpha (7-13 Hz), beta (13-30 Hz), and gamma (>30 Hz) EEG oscillations along with their percent ratios; and 2) spatial heterogeneity, including global functional connectivity and interhemispheric asymmetry in the above-mentioned frequency bands.

For patients with peripheral nerve dysfunction, we will compare the amplitude and latency of the SSEP responses, and the source localization on individual brains between pre- and post-operative visits.

Stroke hdEEG-, EIT-, and EIS-based analysis

The aim of the hdEEG, EIT, and EIS analyses is to investigate how well these technologies function alone or in combination with each other or with other information, such as the NIHSS, CT or MRI-images to aid in 1) discriminating hemorrhagic from ischemic stroke, 2) monitoring of stroke patients, and 3) predicting stroke outcomes.

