Risk of choking: The developed mouthpiece (sterile lattice, Fig. 1B) is designed to conform to the subjects' mouth and can be bit down on, reducing chances of choking. For the alternative standard Ag/AgCl electrode approach each electrode will be tethered outside the mouth at a patient-specific length, reducing chances of choking/swallowing. Furthermore, data recording from these electrodes will be limited to 3-minute windows at the beginning and end of the ~30 minute recording sessions during which time investigators will be closely monitoring the subjects, ensuring that they remain safe.

c. Describe why all the risks to subjects are reasonable in relation to both anticipated benefits and the knowledge expected to be gained from the study:

hdEEG

The cognitive task is designed to investigate the participants' emotion, cognition and attention. The discomfort they may experience will reflect the changes in their emotion, cognition and attention, which is essential in our investigation.

The functional tasks (motor and sensory) are designed to map the subjects' primary motor and somatosensory brain areas. Peripheral nerve stimulation can reliably trigger a robust response in subjects' somatosensory areas. And this protocol has been clinically used both for outpatient neurodiagnostic tests and inpatient intraoperative neuromonitoring purposes. Detailed mapping of the subjects' primary motor and somatosensory areas are very important for certain types of surgical intervention, such as resection or neurostimulator implantation in epilepsy patients.

EIT/EIS

Stroke affects hundreds of thousands of unfortunate victims on a yearly basis and improvements in stroke detection, monitoring, and prognostication could have a significant impact on patient care. The data collected here will represent an important step in determining the potential for EIT/EIS or their combination with MRI/CT and hdEEG and/or MRI/CT for these applications.

7. Unexpected Events or Incidental Findings

Note: It may be important to consider the potential for certain unanticipated events to occur, for example:

- finding an anomaly in a MRI
- discovering child abuse
- causing distress in interviews of a sensitive nature

Describe potential events and provide a plan of action:

In the unlikely event that patients experience a seizure during the study, DHMC staff neurologists/epileptologists ([name] and [name]) will be on site to provide immediate care.

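### Function mapping rests on activation that looks consistent and localized, and no planned analysis compares a task or SSEP source with a known site, so a reproducible but displaced map could go undetected.

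*Combined protocol and SAP*

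**What the plan says.** Section 2 (Objectives and Hypotheses, hdEEG) gives the purpose: to "use the hdEEG for improved localization of critical brain functions", and "also planning surgical intervention if warranted". Section 6.c justifies the motor and sensory tasks on similar grounds, saying that detailed maps of the "primary motor and somatosensory areas are very important for certain types of surgical intervention".

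Section 10.b says the team will, after pilot studies, "focus on those tests which appear to be eliciting consistent, localized brain activation". It continues: "Under these circumstances adequate statistical power should be obtained by repeating these tests in 15-20 patients". It then sets the short-term epilepsy cohort apart, where the main interest is how spike locations relate to other clinical findings.

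Two kinds of localization do have an accuracy check. In Section 4 (hdEEG Processing), intracranial EEG or ECoG, if applicable, "will be used to evaluate the accuracy of IED source localizations". For stroke, Section 4 compares EIS with prior imaging and uses position error for stroke localization.

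The ingredients of a check on function mapping are also present. Section 3 (hdEEG Data Management) adds SSEP tests "in order to reliably activate the somatosensory area during the sensory task" and records them on the hdEEG system. Section 4 builds head models on patients' T1 MRI and defines 84 regions of interest per subject, "defined according to the 42 Brodmann areas (BAs) for the left and right hemispheres".

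**The concern.** A bias from the head model, the co-registration or the inverse solution can shift a source by a similar amount in every patient. The map would then be focal and repeatable, which is what Section 10.b looks for, and still in the wrong place. More patients or more repeats tighten the estimate around the shifted site and give no sign of the shift.

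At stake is the function-mapping aim itself. The study could report that hdEEG localizes function while holding no analysis that could show otherwise, and the stated use of such maps includes surgical planning. Section 3 concedes that the movement-task rhythm is prone to artifact and not specific to the type of movement, which makes an anchor of known location more useful.

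**Working it through.** **1. The plan's own figure.** The 15-20 patients in Section 10.b cannot be reproduced: no endpoint, effect size, SD, significance level or power is given. Under an assumed one-sample t-test at two-sided 0.05, the detectable standardized effects are:

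| n | 80% power | 90% power |
|---|---|---|
| 15 | 0.78 SD | 0.90 SD |
| 20 | 0.66 SD | 0.76 SD |

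Even on that reading, the power is to show that a response exists, not that its site is correct.

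**2. Every planned analysis that touches localization.**

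| Analysis | Applies to | Tests a mapped function site against a reference? |
|---|---|---|
| Intracranial EEG/ECoG (Section 4, hdEEG Processing) | IED sources, if applicable | No |
| Correlation with other clinical diagnostic results (Section 10.b) | Spikes | No |
| Position error; EIS against prior imaging (Section 4) | Stroke | No |
| Pre- versus post-operative SSEP source (Section 4) | Peripheral nerve patients | No: same method at both visits, so a constant bias cancels |
| Regression/ANOVA across hdEEG, EIT, EIS and SSEP metrics (Section 4, Statistical Analyses) | Functional assessment in stroke | No: compares information content |
| Review of progress toward validation (Section 5) | Whole study | No reference, metric or threshold given |

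**3. Why consistency cannot reveal displacement.** On one axis, let the mapped position be the true site plus a constant offset b plus scatter with standard deviation SD. The 95% half-width of the mean position is t(0.975, n-1) × SD / √n, which does not contain b. With an assumed SD of 5 to 10 mm:
- n = 15: 2.145 × 5/√15 = 2.77 mm, to 2.145 × 10/√15 = 5.54 mm
- n = 20: 2.093 × 5/√20 = 2.34 mm, to 2.093 × 10/√20 = 4.68 mm

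These widths are the same for any b. They describe a signed mean on one axis and are not the precision of a distance. A distance cannot be negative: with no bias and equal normal scatter on three axes, the mean distance to a point is SD × √(8/π), that is 5 × 1.596 = 8.0 mm or 10 × 1.596 = 16.0 mm. Distance to a region is zero inside it. Signed offset and distance therefore need separate reporting.

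**4. What a concordance check would give.** Each subject's SSEP peak is scored as inside or outside the expected region, with an exact (Clopper-Pearson) 95% interval. When all n agree, the lower limit is 0.025^(1/n).

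| Agreeing / evaluable (assumed) | Exact 95% interval |
|---|---|
| 5/5 | 47.8%-100% |
| 10/10 | 69.2%-100% |
| 15/15 | 78.2%-100% |
| 20/20 | 83.2%-100% |
| 12/15 | 51.9%-95.7% |
| 16/20 | 56.3%-94.3% |

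The documents do not say how many subjects will have both an SSEP and an own-MRI head model, so the rows span a range.

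**The case against.** The strongest reply is that the Section 10.b sentence is a sample-size remark about where effort will go after pilot work, not an acceptance rule. Section 2 calls task development ongoing, and Section 5 foresees review of progress toward validating the tests. This largely stands. A reader might infer that consistency is the only criterion for keeping a test, or that a displaced map would be accepted. The documents do not support either: Section 3 also ties task choice to the patient's situation, lesion or planned procedure, and no formal acceptance rule is written. What remains is that no planned analysis would detect displacement.

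A reader might also infer that localization is unchecked throughout the study. It is not: IED and stroke localization have checks, and the short-term epilepsy cohort's main rationale is spikes.

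Photogrammetry, per-patient electrode correction and individual head models do address co-registration and head-model error. They reduce likely bias but do not measure what is left, and no document figure supports assuming a large one.

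Finally, Section 2 also wants to study how disease disrupts localization. Keeping only tests that match an expected anatomical region could select against that. This objection is sound and limits the fix to reporting.

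**Conclusion.** The gap is real for function mapping and confined to it. Apparent consistency and focality are unaffected by a constant offset, and none of the analyses listed compares a task or SSEP source with a known site. A displaced map could therefore go undetected. Its actual size is unknown: the millimetre values above rest on an assumed SD of 5 to 10 mm, and the concordance intervals on assumed numbers evaluable.

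An SSEP check would give the study a positive control it now lacks, but only for somatosensory maps. Good SSEP agreement might be read as validating the language, memory, emotion or social-cognition maps. It would not, since it tests one function in one region.

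**What to change.** **Section 4.** Add a descriptive positive control for subjects who have an SSEP recorded on hdEEG, an own-MRI head model, no lesion of the central region and a usable response. For peripheral nerve patients, use an unaffected nerve or report abnormal responses separately. Report the share of early SSEP source peaks in the contralateral primary somatosensory Brodmann region with an exact 95% interval, and the signed offset or distance to that region, labelled as such. State the number evaluable.

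Extend the intracranial EEG/ECoG sentence to task and SSEP sources only where the same task or stimulation was recorded invasively in care.

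**Section 10.b.** Report this agreement alongside consistency, and do not use it as a filter for retaining tests. State that it supports somatosensory maps only, and that accuracy for language, memory, emotion and social-cognition tasks is unverified where no reference exists.

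**Cost.** The SSEP check is analysis and wording only, using recordings, head models and regions already planned. The evaluable number may be small; for example, stroke-study controls use a standard atlas instead of their own MRI. An atlas-defined region is an imperfect reference. The documents do not say whether any task or stimulation will be recorded invasively, so the second part may yield little.
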